**Theoretical Model of Mediation of the Effect of Nightmares on Suicidal Ideation**

The expert workshop on suicide prevention concluded that “randomized controlled trials of psychopharmacology are needed in suicide prevention studies.”{Mann, 2005 819 /id} Targeted treatment of nightmares may represent one such avenue. We show in our Preliminary Studies that (1) the relationship between sleep disturbance and suicidal ideation holds true within the context of depression clinical trials, (2) nightmares and disturbing dreams about sleep mediate risk for suicidal ideation in insomniacs.

**3.c. Innovation**

We reported the first clinical trial examining insomnia and suicide risk.{McCall, 2010 1193 /id} While all pharmacologic interventions targeting suicide risk are innovative and important, targeting nightmares as a modifiable risk factor for suicidal ideation is especially innovative. Despite dozens of reports of association between sleep insomnia and suicide, there are no completed psychopharmacology trials targeting nightmares for suicide risk reduction. Our ongoing study, REST-IT, is the first multi-site intervention for insomnia as a means to reduce suicidal ideation in depressed, suicidal, insomniacs. The present proposal, REST-ON-PTSD, will target treatment for nightmares and disturbing dreams as a second avenue for reducing suicidal ideation. We will test the impact of prazosin on suicidal thinking, and as part of our innovation, we will test whether improvement is mediated via reduction in nightmares and disturbing dreams.

**3.d. How this project will improve knowledge and practice**

This project is consistent with the August 2010 Report of the National Advisory Mental Health Council’s Workgroup, “From Discovery to Cure”, which emphasized the importance of advancing ‘personalized treatment’ and ‘preemptive treatment’ (page 3).{Leon, 1999 1256 /id} The emphasis of this Report is evident in our proposal as we identify nightmares as a symptom of particular relevance in some, but not all suicidal patients, and deserving of targeted intervention, leading to a preemptive reduction in nightmares and disturbing dreams, and presumably, suicidal ideation. In Recommendation 2.4.1, the Report also calls for support for clinical trials which show that (a) “the adaptation [i.e., intervention] changes a factor [nightmares] that has been associated with ....partial response [suicidal ideation], and (b) clear explication of the mechanism by which the moderator variable [nightmares] functions to disadvantage... a subgroup [suicidal PTSD outpatients with nightmares]. This project meets the needs expressed in the Report.

**3.e. Approach****3.e.1 Preliminary Studies****Relationship between insomnia and suicidal ideation during a 10-week clinical trial**

We consented 60 depressed insomniacs to participate in a study examining the value of adding a hypnotic medication to a SSRI.{McCall, 2010 1149 /id} After a week of baseline assessment, patients received one week of open-label fluoxetine (FLX) monotherapy, starting at 20 mg in the morning. Patients still reported insomnia after one week of FLX and continued on with 8 more weeks of open label FLX, and were also randomized to also receive either the hypnotic eszopiclone (ESZ) 3 mg or placebo given on a double-blind

basis at bedtime. Patients who still had a 24-item Hamilton Rating Scale for Depression (HRSD24) {Hamilton, 1960 371 /id}  $>15$  at the end of 4 weeks of randomized treatment could choose to take 40 mg FLX for the next 4 weeks. Study endpoints included measures of sleep, mood, and suicidal ideation. Insomnia severity was graded by the Insomnia Severity Index (ISI). {Bastien, 2001 639 /id} Suicidal ideation was measured with the Scale for Suicide Ideation (SSI). {Beck, 1979 18 /id; Beck, 1997 19 /id; Beck, 1999 20 /id}

Participants were 18-70 years old, with either (a) sleep latency  $> 30$  minutes and sleep efficiency  $< 85\%$  at least 4 nights per week. {Edinger, 2004 553 /id} All participants met a DSM-IV diagnosis of unipolar MDE per Structured Clinical Interview for DSM-IV (SCID), {American Psychiatric Association, 1994 286 /id} and a HRSD24 score  $\geq 20$ . {Hamilton, 1960 371 /id} All participants completed one night of baseline polysomnogram (PSG) which showed no clinically significant sleep apnea (Apnea/Hypopneas index  $>15$ ) or Periodic Limb Movement Disorder (PLM arousal index  $>15$ ), following standard measurement procedures described elsewhere. {McCall, 2009 1052 /id}

The average age of the randomized sample was  $41.5 \pm 12.5$  years, and 66% were women, with 23.2% minorities. At baseline, the average HRSD24 score was  $27.1 \pm 3.9$ , and the average ISI score was  $20.7 \pm 4.0$ . Scale for Suicide Ideation (SSI) scores were analyzed using generalized linear mixed models for repeated measures with predictor variables being insomnia (ISI scores), the mood item, and the anhedonia item from the HRSD24. Baseline SSI was  $3.7 \pm 5.2$ , with 55% having a SSI score  $\geq 1$ , and 37% of patients having a SSI score  $\geq 3$ .

The model with ISI as the predictor for SSI was significant with the regression coefficient corresponding to ISI being positive ( $\beta=0.055$ , SE=0.02,  $p<0.01$ ). Other univariate models found that the depressed mood item was also a significant predictor of suicidal ideation ( $p<0.005$ ), but anhedonia was not a predictor of suicidal ideation ( $p=0.9$ ). A multivariate model simultaneously including both the insomnia and the depressed mood items found that both were independent predictors of suicidal ideation (both  $p<0.05$ ). Our findings confirm that the intensity of insomnia predicts intensity of suicidal ideas during a clinical trial of MDE, even after adjusting for depressed mood and anhedonia. {McCall, 2010 1193 /id}

#### Suicidal ideation is mediated by nightmares

In a new study we have recently reported that the relationship between insomnia and suicide is mediated through nightmares and disturbing dreams. {McCall, 2013 1348 /id} We collected cross-sectional data on 50 adults (mean 55 y.o.) in various stages of active depression or recovery, including 16 psychiatric inpatients and 23 outpatients and 11 emergency psychiatry patients. Bad dreams were measured with the Disturbing Dreams and Nightmare Severity Scale (DDNSI), while the intensity of suicidal ideation was measured with Scale for Suicide Ideation (SSI). {Beck, 1979 18 /id; Beck, 1997 19 /id; Beck, 1999 20 /id} DDNSI was significantly related to SSI ( $r=0.60$ ,  $p<0.001$ ), and in a mediation analysis we found that the relationship between insomnia and suicidal ideation was in fact mediated in part by disturbing dreams and nightmares. These results support the premise that nightmares mediate insomnia as a risk factor for suicidal ideation in depressed patients. Using a receiver operating curve, we also found that emergency psychiatry patients are best discriminated from outpatients by a Scale for Suicide Ideation score of 16, and while the outpatients and emergency patients were best separated by a Disturbing Dreams and Nightmare Severity Scale score of 6 ( $p<0.001$ ).

### METHODS OF THE PRESENT PROPOSAL

#### 3.e.2. OVERVIEW

This pilot study will enroll 20 participants with PTSD who have prominent problem with nightmares and a mild-to-moderate degree of suicidality. Participants will have been on a stable dose of an SSRI or open label treatment for bipolar disorder, at a therapeutic dose, for at least one month before baseline assessment. Patients with bipolar disorder will have been on a stable dose of FDA-approved treatment for bipolar disorder

(lithium, valproic acid, lamotrigine, quetiapine, asenapine, olanzapine, ziprasidone, lurasidone or the olanzapine-fluoxetine combination). Patients who meet all qualifying requirements at baseline will then be randomized in a 1:1 proportion to either prazosin 1 mg at bedtime or placebo. Over the course of 6 weeks, the dose of prazosin will be increased as tolerated, while the dose of the SSRI or medication for bipolar disorder is held constant. Participants will be re-assessed weekly for 8 weeks post-randomization, and only enough prazosin will be provided to last until the next visit.

### **3.e.3. Participants**

**Inclusion criteria:** Participants are 18-65 years of age, including both men and women. The local project manager confirms a DSM-IV-TR diagnosis of PTSD by SCID and by the Clinician Administered PTSD Scale (CAPS).{Weathers, 2001 1377 /id} The participant must have a least a moderate degree of nightmare severity, as indicated by a Disturbing Dreams and Nightmares Scale score of  $\geq 10$ .{Krakow, 2002 1368 /id}

Participants must provide their own written, informed consent. Participants will have a mild-moderate level of suicidal ideation defined as a SSI score  $\geq 3$  but will not have imminent intent to commit suicide consistent with a Columbia-Suicide Severity Rating Scale (C-SSRS) suicidal ideation level of  $< 4$ .{Oquendo, 2003 1018 /id} All participants will have been on a stable dose of a SSRI for at least 4 weeks before baseline assessment, at a dose equivalent to fluoxetine 20 mg (i.e., sertraline 50 mg, paroxetine 20 mg, etc.), or if the patient has a diagnosis of bipolar disorder, they must be on a stable dose of an FDA-approved bipolar medication for at least 4 weeks (lithium  $> 300$ mg daily, valproic acid  $> 500$ mg daily, lamotrigine  $> 50$ mg daily, quetiapine  $> 100$ mg daily, asenapine  $> 10$ mg daily, olanzapine  $\geq 5$  mg, ziprasidone  $\geq 20$  mg, lurasidone  $\geq 40$  mg or the olanzapine-fluoxetine combination)Other psychotropics, including additional antidepressants, mood stabilizers, benzodiazepines, and antipsychotics are permitted as long as no dosage changes are anticipated during the randomized treatment with prazosin. A co-morbid diagnosis of major depression is permitted, as well as diagnoses of generalized anxiety, panic disorder, social phobia, and obsessive compulsive disorder.

Participants sexual orientation and gender will be assessed with the following form:

1. Do you consider yourself to be:

- Heterosexual/straight
- Gay/lesbian/homosexual
- Bisexual
- Not sure
- Decline to state

2. What is your gender? (check all that apply)

- Male
- Female
- Transgender, Male-to-Female (MTF)
- Transgender, Female-to-Male (FTM)
- Transgender, do not identify as male or female
- Not sure
- Decline to state

**Exclusion criteria:** Participants are excluded if they have an active diagnosis of alcohol or substance abuse within the last 90 days, active episode of bipolar mania or hypomania, or lifetime diagnosis of schizophrenia per the SCID. Patients with a clinical diagnosis of major neurocognitive disorder or a MMSE  $\leq 24$ , will be excluded.

Additional exclusion criteria

- History of sensitivity or allergy to prazosin or quinazolines

- History of fainting or syncopal episodes in the last 6 months
- History of hypotension
- Automatic Blood Pressure readings with systolic BP <90, or diastolic <50, either sitting or standing.
- Planned use of sildenafil, tadalafil, or similar erectile dysfunction medications

### 3.e.4. Treatment

#### Dose finding during randomized care

Participants who pass all screening and baseline-week assessments immediately begin one capsule of prazosin 1 mg capsule or a placebo. Study drug will be taken at bedtime. Participants will be called by study-staff after two nights, and if participants do not appreciate an improvement in their disturbing dreams and nightmares after 2 nights, then they are allowed to increase their bedtime study drug to two capsules, following the design of Raskind et al (Table 1).{Raskind, 2013 1474 /id}

REST-ON participants return to the clinic each week for routine follow up and assessment of treatment response, BP, and adverse events. If the patient and research physician judge the benefit of study drug to be inadequate for sleep continuity or nightmares, then the dose may be increased according to the titration schedule below. At any point during the medication titration, upward dosages will not be permitted if: systolic BP <90, or diastolic <50, either sitting or standing, or if the patient has felt faint or near-syncopal, or has had a syncopal attack. The final research visit will be at the end of the eighth week of randomized treatment, and decisions will be finalized at that time of transition to care as usual.

Table1 Prazosin dose titration schedule

Week/Day	Men's Dose	Women's Dose
Days 1-2	1	1
Days 3-7	2	2
Week 2	4	2
Week 3	6	4
Week 4	10	6
Week 5	15	10
Week 6	20	10

#### Calculating the number of study-drug capsules dispensed at each visit

At the time of the first medication dispensation, enough medication will be given to last until the next scheduled visit one-week later, plus three more days in case the visit has to be rescheduled. Thus, at the time of the first dispensation, participants will receive 2 capsules for the first two nights, then 10 capsules for the next 5 nights (in the even that there is inadequate effect from one capsule), then 6 more capsules for three more nights in the event that the one-week follow up must be rescheduled. This means that participants will receive 18 capsules at the time of the first dispensation.

Participants will be asked to bring all remaining study drug to the next visit to estimate adherence and medication usage rates. At the time of the second dispensation at the end of week-one of randomized care, participants will be eligible to increase the dose according to the titration schedule, with additional capsules

available in the event that the second follow up visit is later rescheduled up to three days past the one-week timeframe. Of course, the number of capsules will be less in the event that (1) a lower dosage was found to be effective in treating nightmares in the first week, or (2) there are side effects or hypotension at lower doses.

#### Randomization and blinding

Randomization of the 20 participants will be accomplished with blocked randomization: 5 blocks of two patients each. Blinding will be single blind, as the placebo we will use will be a generic lactose-filled capsule, and we will not attempt to create a matching placebo for the purposes of this pilot study. Our reasons for not making a matching placebo are as follows: (1) prazosin is generic and the physical appearance of the prazosin capsules may be subject to change, (2) the vast majority of participants will not know what generic prazosin looks like and hence will remain blind even if the placebo does not look like generic prazosin, (3) our most important outcome measures are self-report measures and hence not subject to investigator bias, (4) from prior experience, we have learned that creation of matching placebos would incur a minimum expense of about \$1000 - an expense that is unnecessary for our purposes.

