#### Post-randomization care

Participants are referred for standard outpatient management at the end of 8 weeks of randomized care. The blind will be broken by a psychiatrist who is not involved in the patient's care during the study, and depending upon randomized assignment and the response to treatment under randomized assignment, the patient will then have the option of receiving a prazosin prescription at the end of the trial until they re-enter usual care. While study drug and doctor's visits were provided to the participants at no cost during randomization, the cost of medications and doctor's visits will be borne by the participant or their insurance company after they leave randomized care. Weekly phone calls will be made after the last visit until the patient has connected with their care provider.

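### If enrolling staff can recognise an earlier patient's capsules, the fixed block size written in the protocol makes up to half of the 20 assignments predictable before enrolment

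*Combined protocol and SAP*

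**What the plan says.** - **Sample and ratio.** Section 3.e.2 gives the size, "This pilot study will enroll 20 participants with PTSD", and further on the ratio: those who qualify are "randomized in a 1:1 proportion to either prazosin 1 mg at bedtime or placebo".
- **Scheme.** Section 3.e.4, Randomization and blinding: "Randomization of the 20 participants will be accomplished with blocked randomization: 5 blocks of two patients each".
- **Blinding.** Same section: "Blinding will be single blind, as the placebo we will use will be a generic lactose-filled capsule". On making the two products look alike, the plan is explicit: "we will not attempt to create a matching placebo for the purposes of this pilot study". The argument given about capsule appearance concerns patients only: "the vast majority of participants will not know what generic prazosin looks like and hence will remain blind".
- **Capsule handling.** Section 3.e.4, on dispensing: "Participants will be asked to bring all remaining study drug to the next visit to estimate adherence and medication usage rates". Table 2 lists medication accountability among the follow-up tasks. The person who counts the capsules is not named.
- **Who enrols and who is blind.** The project manager confirms the PTSD diagnosis (3.e.3), conducts consent (6.b.2) and rates the HRSD24 while blind (3.e.7). The psychiatrist who gives the C-SSRS is also described as blind (3.e.5).
- **End of treatment.** After week 8, a psychiatrist outside that patient's care breaks the blind. What follows is conditional: "depending upon randomized assignment and the response to treatment under randomized assignment, the patient will then have the option of receiving a prazosin prescription".

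The documents do not say who generates or holds the list, who dispenses, or when an assignment is released relative to the eligibility decision.

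**The concern.** A block of two at 1:1 leaves nothing random about its second place. That does no harm if nobody involved in enrolment can learn the first assignment. Here the block size is in the protocol that staff work from, the two products look different, and leftover capsules return to clinic each week. Section 3.e.4 explains why patients should stay blind but gives no reason why staff would.

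Someone who can foresee the next arm can influence who fills it, through the judgement needed for the SCID, CAPS and C-SSRS or simply through whom to approach and when. Section 3.e.4 relies on the main outcomes being self-reported. That guards against biased rating, but selection happens before any outcome is recorded. With 10 patients per arm, each patient carries one tenth of an arm mean, so steering one or two could shift the effect-size and variance estimates. Those estimates are the stated product of the pilot and will be used to design the later trial (Project Summary; 3.f).

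**Working it through.** **1. The plan's own count.** 5 blocks × 2 patients = 10, not 20, so the stated scheme covers half the sample. Two simple corrections reach 20: 10 blocks of 2, or 5 blocks of 4. Both are carried through below.

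**2. Assignments fixed in advance.** Take a 1:1 block of size 2m and someone who knows the block size and all earlier assignments. The expected number of places already determined is 2m/(m+1) per block.

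- Blocks of 2 (m = 1): 2/2 = 1 per block; × 10 blocks = 10 of 20.
- Blocks of 4 (m = 2): 4/3 per block; × 5 blocks = 6.7 of 20.
- One list of 20 (m = 10): 20/11 = 1.8 of 20.

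**3. Correct guesses.** The best strategy is to guess the arm with more places left, and to toss a coin when they are equal.

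- Block of 2: 0.5 + 1 = 1.5 of 2, or 75%.
- Block of 4: 0.5 + 2/3 + (2/3 × 0.5 + 1/3 × 1) + 1 = 2.83 of 4, or 70.8%.
- One list of 20: enumeration of all balanced sequences gives 12.34 of 20, or 61.7%.

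| Scheme | Fixed in advance | Guessed correctly |
|---|---|---|
| 10 blocks of 2 | 10 (50%) | 15.0 (75%) |
| 5 blocks of 4 | 6.7 (33%) | 14.2 (71%) |
| One 10:10 list | 1.8 (9%) | 12.3 (62%) |

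**4. Which route reveals the first assignment in time?** The accrual period is not given. Assume Poisson accrual of 20 patients over 6, 12, 24 or 36 months (26, 52, 104 or 156 weeks). The chance that the second member of a pair enters at least w weeks after the first is exp(−20w/weeks).

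| Accrual | Returned capsules, w = 1 | Week-8 unblinding, w = 8 |
|---|---|---|
| 6 months | exp(−0.769) = 46% | exp(−6.15) = 0.2% |
| 12 months | exp(−0.385) = 68% | exp(−3.08) = 4.6% |
| 24 months | exp(−0.192) = 83% | exp(−1.54) = 21% |
| 36 months | exp(−0.128) = 88% | exp(−1.03) = 36% |

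Capsules seen at the first weekly return could inform about 4.6 to 8.8 of 10 pairs. Capsules seen at dispensing could inform all of them. Unblinding at week 8 could inform about 0 to 3.6 of 10 pairs, so it is the minor route.

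**5. Price of a single list if enrolment stops at 10.** SD of one arm's count = √(10 × 0.25 × 10/19) = 1.15. The chance of a 7:3 or worse split is 2 × (1 + 100 + 2,025 + 14,400)/184,756 = 18%. Blocks of two would give 5:5.

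**The case against.** The strongest reply is that the documents describe the project manager and the study psychiatrist as blind. Prediction requires that the enrolling person knows the block size, knows who is first in the pair, and has seen and recognised that patient's capsules. Nothing says that enrolling staff handle capsules. This stands. A reader might infer that the second assignment of every pair is known in advance, or that half of the assignments are in fact unconcealed; the documents do not support either. What they show is a scheme that is predictable once capsules are seen, together with a claim of blindness for which no means is given.

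A reader might also treat the week-8 unblinding as a main leak. It is done by someone outside that patient's care, the documents do not say that the result reaches enrolling staff, and it usually comes after the partner has entered unless accrual is slow.

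The room for steering is also limited. The SSI and DDNSI thresholds are self-rated, the blood-pressure limits are numeric, and qualifying patients start study drug at once. Judgement in the diagnostic interviews and in whom to approach remains.

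Finally, this is a small pilot on a small budget. That explains the unmatched capsules, which section 3.e.4 justifies partly by a cost of about $1000. It does not explain the block size, since a less predictable list needs no matching placebo.

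**Conclusion.** The concern holds in conditional form. If blocks are of two, and enrolling staff know this and can recognise earlier capsules, up to 10 of 20 assignments are fixed in advance and 75% can be guessed. If blocks of four were intended, the figures are about 6.7 of 20 and 71%. Section 3.e.4 does not settle which, because its own count reaches only 10 patients. All of these figures assume knowledge of every earlier assignment, so they are upper limits and not estimates of what will happen. The size of any resulting bias in the effect estimate cannot be derived from the documents. The change is worth making because the weakness is avoidable at almost no cost and bears on the estimates that the pilot exists to provide.

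**What to change.** In section 3.e.4:

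1. Correct the block count so that the scheme covers 20 patients.
2. Replace the fixed blocks of two with one permuted 10:10 list of 20, or with randomly varied block sizes that are not disclosed to enrolling staff.
3. Have the list held, and capsules dispensed and counted, by existing personnel who neither enrol nor rate any trial patient. The psychiatrist who breaks the blind qualifies only if this is true for all patients; the protocol says only that this person is outside the care of the patient concerned.
4. Release each assignment only after eligibility is recorded.

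The cost is a new list, a few sentences and an agreed division of tasks. The two allocation options differ. The single list lowers the guess rate most, but carries the 18% chance of a 7:3 or worse split if enrolment stops at 10. Varied blocks limit that: with sizes of two and four, the arms can never differ by more than two patients. However, someone tracking the running balance would still guess (1.5 + 2.83)/6 = 72% correctly with equal numbers of each size. Even the single list leaves 62% to a fully informed guesser. Keeping capsules away from enrolling staff (item 3) therefore matters as much as the list.

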#### 3.e.5. Measurement of Suicidal Ideation and Behavior

The Scale for Suicide Ideation (SSI) consists of 19 items that evaluate active suicidal desire, specific plans for suicide, and passive suicidal desire.{Beck, 1979 18 /id;Beck, 1997 19 /id;Beck, 1999 20 /id} Each item is rated by the patient on a 3-point scale from 0 to 2 for a maximum score of 38; a lower score indicates less severe suicidal ideation. The SSI will be collected at baseline and at weeks 1, 2, and 4 of randomized treatment, and once by telephone one month after completing randomized treatment. An SSI score >2 predicts increased risk for suicide death over a period of years.{Brown, 2000 314 /id} The SSI will be collected at the start of each visit, before the participant is seen by the study psychiatrist.

The Columbia-Suicide Severity Rating Scale (C-SSRS){Oquendo, 2003 1195 /id} is based upon the Columbia Classification Algorithm of Suicide Assessment(C-CASA).{Posner, 2007 932 /id} This C-SSRS is used by the FDA in clinical trials to assess suicide risk, and includes a structured assessment of past or recent suicidal behavior. It will be administered at each visit by a study psychiatrist blinded to treatment assignment. C-CASA has excellent inter-rater reliability in classifying suicide attempts, with an overall intra-class correlation coefficient of 0.89.

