#### 3.e.7. Measurement of Depression

Depression severity will be tracked by the observer-rated 24-item HRSD. {Hamilton, 1960 371 /id;Beck, 1988

337 /id} The HRSD24 will be administered by same project manager, blind to treatment assignment, at baseline and thereafter at weeks 1, 2, and 4 of randomized treatment. Research staff will demonstrate inter-rater reliability  $> 0.85$  against a criterion-set of clinical videotapes. The HRSD24 has three sleep items and one suicide item. The HRSD will be recorded as the total score (HRSD24), and will also be analyzed without the three sleep items or the suicide item (HRSD20). The three insomnia items and the suicide item will be separately examined.

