### 3.e.8. Measurement of nightmares: The Disturbing Dreams and Nightmare Severity Scale

The frequency and intensity of disturbing dreams and nightmares will be measured with the Disturbing Dreams and Nightmare Severity Scale (DDNSI). This scale is derivative of a simpler Nightmare Frequency Questionnaire that had a test-retest weighted kappa  $> 0.85$ . {Krakow, 2002 813 /id} The revised DDNSI has good internal consistency with a Cohen's alpha  $> 0.80$ . {Bernert, 2005 798 /id; Bernert, 2009 1044 /id} A DDNSI score  $> 10$  indicates a clinical nightmare disorder. {Krakow, 2002 1368 /id} Each participant will complete this self-report scale.

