### 3.e.13. Salivary amylase

In humans,  $\alpha$ -amylase levels are highest in pancreatic and salivary secretions. Increased salivary amylase activity is a marker for increased sympathetic nervous system activity. {Nater, 2009 1466 /id} We will collect samples of saliva at baseline and each follow up visit. The tubes containing the samples will be vortexed, centrifuged at 2000xg at 4 C for 10 minutes, and the saliva will be aliquoted and frozen at -80C for future

analysis. On the day of the assay, the samples will be thawed and will be centrifuged once more to assure that solids are removed from suspension. Salivary amylase activity will be determined using the Amylase Activity Assay kit (Sigma). In this kit, amylase activity is determined using a coupled enzymatic assay, which results in

	Baseline of REST-ON	Follow up Visits in REST-ON	
Evaluation to sign consent	1		
Consent	2		
Registration	3		
Demographics	4		
Visual Analogue scales for nightmare descriptors	5		
Vitals with orthostatic BP	6	1	
PCL-S	7	2	
SCID and CAPS	8		
Hamilton Rating Scale for Depression (HRSD)	9	7	
Beck Suicide Severity Index (SSI)	10	3	
Columbia-Suicide Severity Rating Scale	11	4	
Disturbing Dreams and Nightmare Severity Index	12	5	
Insomnia Severity Index	13	6	
Concomitant Medications	14	8	
CGI-S	15	9	
CGI-I	16	10	
Adverse events		11	
Encounter Disposition Form- Baseline/Baseline Follow-up	17	12	
Study Medication Accountability		13	
Salivary amylase	18	14	
	Baseline of REST-ON	Follow up Visits in REST-ON	
Evaluation to sign consent	1		
Consent	2		
Registration	3		
Demographics	4		
Visual Analogue scales for nightmare descriptors	5		
Vitals with orthostatic BP	6	1	
PCL-S	7	2	
SCID and CAPS	8		
Hamilton Rating Scale for Depression (HRSD)	9	7	

Table 2 – Order of Assessments for REST-ON-PTSD

Beck Suicide Severity Index (SSI)	10	3
Columbia-Suicide Severity Rating Scale	11	4
Disturbing Dreams and Nightmare Severity Index	12	5
Insomnia Severity Index	13	6
Concomitant Medications	14	8
CGI-S	15	9
CGI-I	16	10
Adverse events		11
Encounter Disposition Form- Baseline/Baseline Follow-up	17	12
Study Medication Accountability		13
Salivary amylase	18	14

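### Self-report does not rule out clinician influence: Table 2 puts the nightmare scale (DDNSI) directly after the psychiatrist's interview, while the SSI is protected by being taken first

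*Combined protocol and SAP*

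**What the plan says.** The Randomization and blinding part of section 3.e.4 calls the trial single blind. The placebo is a generic lactose capsule that is not made to look like prazosin, and four reasons are given. The third is that "our most important outcome measures are self-report measures and hence not subject to investigator bias".

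For the primary outcome, section 3.e.5 adds a safeguard: "The SSI will be collected at the start of each visit, before the participant is seen by the study psychiatrist". The same section says of the C-SSRS: "It will be administered at each visit by a study psychiatrist blinded to treatment assignment".

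For the DDNSI, section 3.e.8 says only "Each participant will complete this self-report scale" and gives no rule on when in the visit this happens. The DDNSI measures the construct of the Secondary Aim and Hypothesis 2. It also supplies the mediator: section 3.c promises that "we will test whether improvement is mediated via reduction in nightmares and disturbing dreams", and section 3.f plans the mediation analysis.

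Table 2, titled "Order of Assessments for REST-ON-PTSD", numbers the follow-up items. The SSI is 3rd, the C-SSRS 4th, the DDNSI 5th and the ISI 6th.

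**The concern.** Self-report and freedom from clinician influence are different properties. When the participant fills in the form, no rater can score it leniently. The participant's answers can still be coloured by a clinician's manner, expectations or remarks a few minutes earlier. In a single-blind trial with capsules that differ in appearance, the plan cannot assume that no clinician will form a belief about the assignment.

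The plan appears to recognise this, because it takes the SSI before the psychiatrist is seen. The same protection is missing for the DDNSI, where it matters almost as much. Nightmares are also what titration is steered by: the dose may go up "If the patient and research physician judge the benefit of study drug to be inadequate for sleep continuity or nightmares".

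The pilot exists to supply effect sizes, variances and correlations for a larger trial. If a clinician's cue moved the DDNSI and not the SSI at the same visit, the shift could not later be told apart from a drug effect on nightmares. It would enter both the secondary estimate and the mediation analysis.

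**Working it through.** The plan gives no figure to reproduce, and no bias can be calculated. The check is a comparison of the stated order with the stated safeguard.

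**Step 1: who completes each instrument, and when.** Positions are from Table 2; the person is from sections 3.e.5 to 3.e.9.

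| Item | Completed by | Follow-up now | Follow-up proposed | Baseline now | Baseline proposed |
|---|---|---|---|---|---|
| PCL-S | participant | 2 | 2 | 7 | 7 |
| SSI | participant | 3 | 3 | 10 | 10 |
| C-SSRS | psychiatrist | 4 | 6 | 11 | 13 |
| DDNSI | participant | 5 | 4 | 12 | 11 |
| ISI | participant | 6 | 5 | 13 | 12 |
| HRSD | project manager | 7 | 7 | 9 | 9 |
| Medication accountability | not stated | 13 | 13 | none | none |

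**Step 2: count the self-report scales on each side of the C-SSRS at follow-up.** Before it: PCL-S and SSI, 2 of 4. After it: DDNSI and ISI, 4 − 2 = 2 of 4. Under the proposed order the counts are 4 before and 0 after.

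**Step 3: compare with the written rules.** The SSI's position (3rd) agrees with its rule in 3.e.5. The DDNSI's position (5th) would break the same rule if 3.e.8 contained it. A site that follows the plan exactly therefore collects the DDNSI after psychiatrist contact at each follow-up visit where both are done. Section 3.f has outcomes collected weekly for 8 weeks, so that is up to 8 visits per participant. Section 3.e.8 gives no schedule of its own.

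**Step 4: place the dose discussion.** Table 2 gives it no position. Section 3.e.4 bars an increase after low blood pressure, faintness or syncope. Blood pressure is taken 1st and adverse events are reviewed 11th. If the check for faintness is part of the adverse-event review, the dose decision falls after the DDNSI. That is likely, but not stated.

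**Step 5: what reordering can and cannot remove.** It removes influence from psychiatrist contact earlier in the same visit. It does not remove expectations carried over from previous visits, which can reach the SSI and the DDNSI alike. Nor does it prevent unmasking by side effects: section 3.a cites nasal congestion in 22% on prazosin against 11% on placebo.

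**The case against.** The strongest reply is that the psychiatrist giving the C-SSRS is declared blinded, and that harm needs a chain of events that nobody has shown. The psychiatrist would have to see capsules, tell the two kinds apart, keep that belief and convey it during a structured interview. The participant would then have to change nightmare answers minutes later. Dose discussion, the likeliest channel, probably comes later in the visit anyway. The primary scale is already protected, the trial has 20 participants, and section 3.f itself cautions that the sample is small for mediation. All of this stands, and it is why the point is minor. It does not explain why one key self-report scale is taken before the psychiatrist and the other after.

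A reader might be tempted to infer more:

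- **That the raters are unblinded.** Sections 3.e.5 and 3.e.7 say the opposite ("The HRSD24 will be administered by same project manager, blind to treatment assignment"). The plan does not say how these raters are kept from seeing unmatched capsules, but undescribed handling is not exposure. Table 2 puts the capsule count 13th, after every rating of that visit, although this does not protect later visits. Reason (3) also does not cover rater-scored scales, so it makes no false claim about them.
- **That the C-SSRS psychiatrist also sets the dose.** Section 3.e.4 names a research physician, and section 6.d speaks of psychiatrists in the plural. The documents do not settle whether they are the same person.
- **That the DDNSI effect is inflated.** Multiplying 8 visits by 20 participants gives 160 DDNSI completions after psychiatrist contact, but that counts contact with someone described as blinded. It does not count biased answers.

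**Conclusion.** The concern holds as a minor, avoidable weakness. Reason (3) claims more than self-report can deliver. As the order of assessments stands, the DDNSI and the ISI lack the same-visit protection that the plan gives the SSI: two of four self-report scales, at every follow-up visit run in Table 2's order.

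This rests on reading Table 2's numbers as the sequence within the visit, as its title says, and on the C-SSRS being the psychiatrist's interview, as 3.e.5 and 6.d say. If staff in fact hand out all self-report forms together before the psychiatrist is seen, practice is already sound and only the document is wrong.

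No size or direction of bias can be given. The documents contain no DDNSI standard deviation and nothing on how often, or which way, a clinician's cue would move the score. The case for acting is that the correction costs almost nothing and the pilot's estimates feed the next trial.

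**What to change.** 1. In Table 2, move the follow-up C-SSRS from 4th to 6th, giving PCL-S 2, SSI 3, DDNSI 4, ISI 5, C-SSRS 6. Items 7 to 14 stay. At baseline move it from 11th to 13th, so that the order is alike throughout.
2. In section 3.e.8, add a sentence such as: *Participants complete the DDNSI before any contact with the study psychiatrist at that visit and before any discussion of dose.*
3. In the blinding section, limit reason (3) to the claim that self-report measures are not subject to rater scoring bias.

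The cost is one moved row and two changes of wording, with no new visit, measure or staff. The C-SSRS starts two short scales later in the same visit, and the SSI keeps its place. Because section 6.d lists the DDNSI among the scales that inform withdrawal decisions, having it completed before the psychiatrist's interview also helps there.

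As a separate suggestion, on which the point above does not depend, reconcile the single-blind label with the two raters described as blinded by stating who is blinded. Where existing staffing allows, have someone who does no ratings dispense, collect and count the capsules. The documents do not name the dispenser, so whether such a person is available is an assumption. A matching placebo is not requested.
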